12.3 Sample Size and Power Estimate

For this phase 2 study, the primary endpoint is the change of B cells between the pre-treatment biopsy and post-treatment RP specimen. Each patient's response to neoadjuvant ibrutinib will be a binary classification. Patients will be considered to have a

“positive” response if there is >2 fold decrease in the number of B cells, or considered to have a “negative” response if there is <2 fold decrease in the number of B cells. The accrual of 18 patients to the phase 2 trial and incorporation of 6 patients who received ibrutinib at MTD in the safety lead-in (a total of 24 evaluable subjects) will be sufficient to determine whether 20% or more of the cohort achieves this 2 fold decrease in B cells, compared to a null response of 5% or less of a reference group of patients who underwent RP without neoadjuvant treatment. This comparison has a power of 0.818 at a significance level of 0.044 based on a one-sided binomial exact test. If 4 more evaluable patients show a “positive” response, the treatment achieves the expected “response” rate of 20%.

The safety-run in will require 6 patients (with a potential for 6-12 more if dose de-escalation is required). The Phase II study will require a total of 24 patients on MTD and thus 18 additionally enrolled patients besides the 6 on MTD during the safety lead-in.

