12.4 Replacement Policy

All patients who receive a dose of ibrutinib will be analyzed for safety and efficacy. Subjects who discontinue from study participation prior to receiving any dose of study therapy may be replaced. Subjects who have received any dose of study therapy will not be replaced for the safety and efficacy endpoints. Patients removed from study for unacceptable treatment related adverse event(s) will be followed until resolution or stabilization of all treatment related AEs to grade 2 or lower. However, they will not be replaced. Patients enrolled during the safety lead-in who discontinue treatment during the DLT observation period for reasons other than a DLT will need to be replaced for DLT purposes.

Because there is a potential for loss of immune cell infiltration within the prostate tissue after >12 days of not receiving ibrutinib, any patient who undergoes RP after 12 days from the last dose of ibrutinib (i.e. from scheduling delay of RP) will be included in the final analysis; however, an additional patient will be accrued as replacement. This will keep the treatment uniform in order to evaluate for immune response. The maximum number of allowed replacement patients for delayed RP is 4.

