12.6.2.2 Intratumoral Immune Infiltration

For all subjects, immune cell subsets and localization will be summarized by changes from baseline to after treatment. Patients will be considered to have a positive response if there is ≥ 2 fold decrease in the number of B cells, or considered to have a negative response if there is < 2 fold decrease in the number of B cells. The proportion of patients who have “positive” responses will be reported, with 95% confidence intervals. Descriptive statistics will be used to describe pre-treatment biopsy immune infiltration, post-treatment RP immune infiltration, and immune infiltration of reference RP tissue.

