12.9 UCSF's Data

Data from the first three patients enrolled at UCSF will be shared with Washington University under a Data Use Agreement and analyzed under the auspices of this study.

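### The stated power of 0.818 and alpha of 0.044 do not hold for 24 patients (exact values 0.736 and 0.030), and 4 responders of 24 is 16.7%, not 20%

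*Combined protocol and SAP*

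**What the plan says.** Section 12.3 defines the phase 2 primary endpoint as a binary response, a two-fold decrease in B cells from biopsy to prostatectomy. It combines 18 new patients with 6 from the safety lead-in, "a total of 24 evaluable subjects", and repeats the number: "The Phase II study will require a total of 24 patients on MTD". This sample "will be sufficient to determine whether 20% or more of the cohort achieves this 2 fold decrease in B cells", against a null of 5% or less. The operating characteristics follow: "This comparison has a power of 0.818 at a significance level of 0.044 based on a one-sided binomial exact test". The success rule begins "If 4 more evaluable patients show a" and ends by saying that the treatment has then reached the expected 20% rate. I read the garbled opening as at least 4 patients.

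Three other places bear on the same test:

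- Section 12.6.2.2 says that the proportion of positive "responses will be reported, with 95% confidence intervals". It names neither the interval method nor a test.
- Section 12.4 says that a patient operated on more than 12 days after the last dose "will be included in the final analysis; however, an additional patient will be accrued as replacement", up to 4 replacements. Sections 12.4 and 12.6.1 analyse everyone dosed for efficacy.
- Section 12.9 says: "Data from the first three patients enrolled at UCSF will be shared with Washington University under a Data Use Agreement and analyzed" under this study. Section 3.2 records that these three received 840 mg for 2 weeks. The Abstract places the 24 at 840 mg/d for 4 weeks.

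**The concern.** Section 12.3 fixes every input to an exact single-arm calculation, so its power and alpha can be checked directly, and they do not follow from those inputs. They are the justification for the trial's size, and the 4-responder cut-off is the only decision rule given for the primary efficacy endpoint. If power is overstated, the trial is more likely than its readers believe to miss the effect it was built to find.

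The sentence about 20% has a separate consequence. A result of 4 responders would be written up as having reached a rate that was not observed.

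Finally, a cut-off fixed at 4 has the stated properties only for a fixed denominator, and the plan leaves the denominator open.

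**Working it through.** **Inputs (Section 12.3).** n = 24, null p0 = 0.05, alternative p1 = 0.20, one-sided exact binomial test, success if X ≥ 4.

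**Formulas.** For X ~ Bin(n, p), alpha = P(X ≥ r | p0) and power = P(X ≥ r | p1).

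**Planned design, n = 24, r = 4.**

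- Alpha = 1 − (0.2920 + 0.3688 + 0.2232 + 0.0862) = 0.0298
- Power = 1 − (0.0047 + 0.0283 + 0.0815 + 0.1493), which is 0.7361 before the terms are rounded

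**Can another cut-off at 24 give the stated figures?**

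| Cut-off (n = 24) | Alpha | Power |
|---|---|---|
| at least 3 | 0.1159 | 0.8855 |
| at least 4 | 0.0298 | 0.7361 |
| at least 5 | 0.0060 | 0.5401 |

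No row has alpha 0.044 or power 0.818.

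**Where the stated pair does arise.** A search over n from 10 to 59 and r from 1 to 14 finds one combination that rounds to both figures: n = 27, r = 4, with alpha 0.0437 and power 0.8177. A two-sample reading (24 treated against the 12 reference patients) does not explain the figures. It gives power of about 0.26 (pooled z, one-sided, alpha 0.044) or 0.11 (Fisher, one-sided, alpha 0.05).

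**Size of the error.** The chance of missing a true 20% rate is 1 − 0.736 = 0.264, against 1 − 0.818 = 0.182 as stated. With 24 patients and r = 4, power reaches 0.80 only at a true rate of about 21.8%.

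**The 20% sentence.** 4/24 = 16.7%, and even 4/27 = 14.8%. An observed rate of at least 20% needs 5 of 24 (20.8%). As a decision rule, 5 of 24 would have power 0.540.

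**Rule against interval at exactly 4 of 24.** The one-sided exact p-value is 0.030, so the rule rejects 5%. The two-sided 95% Clopper-Pearson interval is 4.7% to 37.4%, which includes 5%. The one-sided 95% lower bound is 5.9%, which agrees with the rule.

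**Alpha if the denominator grows and the cut-off stays at 4.**

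| Analysed | How it could arise | Alpha |
|---|---|---|
| 24 | as planned | 0.030 |
| 27 | 24 + 3 UCSF patients | 0.044 |
| 28 | 24 + 4 replacements | 0.049 |
| 31 | 24 + 4 + 3 | 0.067 |

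**The case against.** The strongest defence is that 0.818 can be obtained with 24 patients. The uncorrected one-sided normal (score) approximation at a nominal alpha of 0.044 gives power 0.8179. That does not save the statement, because the plan specifies an exact test. The exact test at 24 cannot have size 0.044, whereas 27 patients reproduce both figures. It does mean that the origin of the figures is unproven. That someone counted 24 plus the three UCSF patients is a guess, and the finding does not depend on it.

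Four further points have some force:

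- **Direction of the error.** True alpha at 24 is lower than stated (0.030 against 0.044). The fault is overstated power, not extra false positives, unless the denominator grows.
- **Interval method.** Section 12.6.2.2 names none. At 4/24 the Wilson (6.7% to 35.9%), Agresti-Coull (6.1% to 36.5%) and Jeffreys (5.9% to 34.9%) intervals exclude 5%. The exact and Wald intervals include it. The conflict therefore depends on the method, although the exact interval is the natural partner of an exact test.
- **Denominator.** Section 12.9 does not say that the UCSF patients enter the 24-patient test. Without them the largest number is 28, where alpha is still below 0.05. The 0.067 needs both pooling and all 4 replacements.
- **Other tests.** Section 12.6.3.2 also tests the pT0 rate by a binomial test, so the B-cell rule is the only primary efficacy rule, not the only efficacy test.

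None of these changes the exact values for 24 patients.

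**Conclusion.** The concern holds and should be corrected. For the 24 patients planned, with success at 4 or more responders, the exact one-sided alpha is 0.030 and the power at 20% is 0.736, below 0.80 and 8.2 percentage points under the stated 0.818. Four responders of 24 reject a rate of 5% or less, but the observed rate is 16.7%.

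These results rest on reading the cut-off as at least 4 and on the exact test that Section 12.3 names. The clash between rule and interval at the threshold also assumes a two-sided exact interval. The alphas for 27, 28 and 31 patients are conditional on how the unsettled denominator is resolved.

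**What to change.** In Section 12.3, state that a rate of 5% is rejected if at least 4 of 24 patients respond, with exact one-sided alpha 0.030 and power 0.736 at a true rate of 20%. Replace the last sentence of that paragraph with one saying that 4 of 24 (16.7%) rejects a rate of 5% or less.

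In Section 12.6:

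- Define the primary denominator as the patients on the 840 mg/d 4-week regimen, on which the 24 are planned, and report the three 2-week UCSF patients separately.
- Say how delayed-surgery patients and their replacements count in the primary test. If the evaluable number is not 24, re-derive the cut-off from the exact binomial.
- Name the interval method, and report the exact one-sided p-value and one-sided 95% lower bound (5.9% at 4/24) beside the two-sided interval.

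The cost is wording and a less favourable power statement, with no extra patients. If the sponsor wants to keep 0.818 and 0.044, the alternative is to plan for 27 evaluable patients. That would mean 3 more patients than now planned, if all are to be on the 4-week regimen.

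### Section 12.3 reads its responder cut-off as achieving a 20% response rate, but a test against a 5% null supports only a rate above 5%

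*Combined protocol and SAP*

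**What the plan says.** Section 12.3 classifies each patient as a responder or non-responder by a two-fold fall in B cells and counts "a total of 24 evaluable subjects". The comparison is stated as "compared to a null response of 5% or less of a reference group of patients who underwent RP without neoadjuvant treatment", and its operating characteristics as "This comparison has a power of 0.818 at a significance level of 0.044 based on a one-sided binomial exact test".

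Two statements in the same paragraph go further than that test. The design "will be sufficient to determine whether 20% or more of the cohort achieves this 2 fold decrease in B cells". And the decision sentence, whose condition is printed as 4 more evaluable patients with a positive result, ends: "response, the treatment achieves the expected “response” rate of 20" per cent.

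Section 12.6.2.2, the analysis section for this endpoint, asks for the proportion of responders with 95% confidence intervals. It repeats neither the test nor the cut-off, and does not say how to interpret the result. The only success statement for the primary immune endpoint is therefore the one in 12.3.

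**The concern.** A single-arm test of 5% against 20% uses the two rates differently. The 5% is the hypothesis that can be rejected, and the significance level limits the error of rejecting it wrongly. The 20% is the rate at which power is evaluated. Crossing the cut-off supports the statement that the rate exceeds 5%. No printed error rate limits the chance of wrongly stating that the rate is 20%.

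Section 12.3 attaches the second statement to the first test. A study team following the text literally could claim a level of activity that the design was not built to show. The claim could rest on data that barely separate the rate from 5%.

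**Working it through.** **Inputs.** All are from 12.3 unless noted: n = 24; null p0 = 0.05; power rate p1 = 0.20; one-sided exact binomial test; printed alpha 0.044 and power 0.818. The text prints 4 more, which is read here as 4 or more (assumption). True rates of 10% and 15% are illustrative values between the plan's own 5% and 20%. Section 12.4 keeps late-surgery patients in the analysis and also replaces up to 4 of them, so n could reach 24 + 4 = 28.

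**Step 1: the plan's own figures.** The probability of reaching cut-off r is

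P(X ≥ r | n, p) = 1 − Σ_{k=0}^{r−1} C(n,k) p^k (1−p)^{n−k}.

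For n = 24, r = 4, p = 0.05, the terms for k = 0 to 3 are 0.2920 + 0.3688 + 0.2232 + 0.0862 = 0.9702, so alpha = 0.030. At p = 0.20 the power is 0.736. The printed 0.044 and 0.818 are not reproduced at n = 24: r = 3 gives 0.116 and 0.886, and r = 5 gives 0.006 and 0.540. In a search over n = 20 to 39 and r = 2 to 7, only n = 27 with r = 4 returns both (0.0437 and 0.8177). That mismatch is a separate matter. Here it supports reading the cut-off as 4 or more, and it makes n = 27 a sensible sensitivity case.

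**Step 2: how often the cut-off is reached.**

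| True rate | ≥4 of 24 | ≥5 of 24 | ≥4 of 27 | ≥4 of 28 |
|---|---|---|---|---|
| 5% | 0.030 | 0.006 | 0.044 | 0.049 |
| 10% | 0.214 | 0.085 | 0.282 | 0.305 |
| 15% | 0.495 | 0.287 | 0.593 | 0.623 |
| 20% | 0.736 | 0.540 | 0.818 | 0.840 |

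At a true rate just under 20% (19.9%), the ≥4 of 24 rule is met with probability 0.732.

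**Step 3: what a result at the cut-off shows.** 4/24 = 16.7%, which is below 20% even as an observed share. The exact two-sided 95% limits solve P(X ≥ 4 | 24, L) = 0.025 and P(X ≤ 4 | 24, U) = 0.025, giving 4.7% to 37.4%. The one-sided 95% lower bound solves P(X ≥ 4 | 24, L) = 0.05, giving 5.9%. At 5/24 (20.8%) that bound is 8.6%, so raising the cut-off by one would not make a 20% claim sound either.

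**Step 4: what a 20% claim would need.** To reject a rate of 20% or less at one-sided 0.05 with n = 24, P(X ≥ r | 24, 0.20) must be at most 0.05. For r = 8 it is 0.089, and for r = 9 it is 0.036. That would take 9 responders, where the one-sided lower bound is 21.2%. This only shows the distance between the two claims. It is not a proposed cut-off.

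**The case against.** The best defence is that the test is properly specified in the same paragraph. The null, the power rate and the method are all there, and the clause about 20% runs straight on to the comparison with 5%. On that view the last sentence, which calls 20% the expected rate, is shorthand for the cut-off having been met. The probabilities of 0.21 and 0.50 are the normal power curve of any 5% versus 20% design. This much stands: test, cut-off and design are not at fault, and the figures describe correct rejections of 5%. They become false statements only through the conclusion the plan prints.

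A reader might infer that a borderline result would simply be reported as a 20% response rate. The documents do not support that. Section 12.6.2.2 requires the observed proportion with its 95% CI, so 4/24 would appear as 16.7% with limits of 4.7% to 37.4%. A careful reader would see how little that excludes.

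A reader might also infer that a go/no-go decision hangs on the sentence. Section 1.3 and the synopsis say only that findings may justify further exploration of ibrutinib in prostate cancer. Neither ties a decision to 4 responders or to 20%.

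The shorthand defence does not remove the point. If 20% means the true rate, the test does not show it. If it means the observed share of the cohort, 4/24 falls short of it.

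**Conclusion.** The point holds as a fault in the stated conclusion. Section 12.3 tests against 5% and says 20% is achieved, and no other section corrects this. With 4 or more of 24, the cut-off is reached in about 21% of trials at a true rate of 10% and 50% at 15%. If 20% is then declared, those are the frequencies of a false statement.

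The size depends on two readings that the text leaves open. It is 9% to 29% if the cut-off is 5 or more, 28% to 59% at n = 27, and 31% to 62% if all four replacements bring n to 28. The conclusion that the test supports only a rate above 5% depends on none of these. It would be wrong to quote 21% to 50% as the error rate of the test itself: against its own null, the error at n = 24 is 0.030.

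**What to change.** Make two wording changes in section 12.3.

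- Replace the last sentence of the decision rule with: *If 4 or more evaluable patients respond, the null hypothesis that the response rate is 5% or less is rejected; 20% is the rate assumed for power, and rejection does not establish a rate of 20%.* This also settles what 4 more means.
- Reword the clause on what the sample can determine to: *to test whether the response rate exceeds 5%, with power computed at a true rate of 20%.*

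Interpret the result with the proportion and 95% CI already planned in 12.6.2.2. A one-sided 95% lower bound beside it is optional. Its one advantage is that it matches the one-sided test: at 4/24 it is 5.9%, whereas the two-sided interval starts at 4.7% and includes the null.

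The printed alpha and power do not belong to n = 24 with this cut-off, and the new wording does not cure that. They are best reconciled in the same edit.

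The cost is two sentences of protocol text, with no change to sample size, cut-off or procedures. The downside for the sponsor is a less favourable success claim.

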12.4 Replacement Policy

All patients who receive a dose of ibrutinib will be analyzed for safety and efficacy. Subjects who discontinue from study participation prior to receiving any dose of study therapy may be replaced. Subjects who have received any dose of study therapy will not be replaced for the safety and efficacy endpoints. Patients removed from study for unacceptable treatment related adverse event(s) will be followed until resolution or stabilization of all treatment related AEs to grade 2 or lower. However, they will not be replaced. Patients enrolled during the safety lead-in who discontinue treatment during the DLT observation period for reasons other than a DLT will need to be replaced for DLT purposes.

Because there is a potential for loss of immune cell infiltration within the prostate tissue after >12 days of not receiving ibrutinib, any patient who undergoes RP after 12 days from the last dose of ibrutinib (i.e. from scheduling delay of RP) will be included in the final analysis; however, an additional patient will be accrued as replacement. This will keep the treatment uniform in order to evaluate for immune response. The maximum number of allowed replacement patients for delayed RP is 4.

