12.6 Analyses Plans

12.6.1 Analysis Population

All patients who receive a dose of ibrutinib will be analyzed for safety and efficacy. Subjects who discontinue from study participation prior to receiving any dose of study therapy may be replaced after discussion with the Study Monitor. Subjects who have received any dose of study therapy will not be replaced.

Demographic and baseline characteristics will be summarized by each cohort and overall. In general, frequency distribution and percentage will be used to summarize categorical measurements, while mean with standard deviation and median with range will be used to describe symmetric and skewed continuous measurements, respectively. Univariate analysis among variables will be assessed using the two-sample t-test, Wilcoxon-rank-sum test, Chi-square test, as appropriate.

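### Men with late prostatectomy are both kept and replaced, so the analysed n can run from 24 to 28 under one cutoff of 4 responders whose stated alpha and power fit only n = 27

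*Combined protocol and SAP*

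**What the plan says.** - **Design (12.3).** The test set is 6 lead-in men plus 18 more, "a total of 24 evaluable subjects". The section adds: "The Phase II study will require a total of 24 patients on MTD". The alternative is a 20% responder rate, "compared to a null response of 5% or less".
- **Operating characteristics (12.3).** "This comparison has a power of 0.818 at a significance level of 0.044 based on a one-sided binomial exact test". The cutoff follows: "If 4 more evaluable patients show a" positive response, which I read as 4 or more. No other cutoff is given for any other n.
- **Late RP (12.4, and the same rule in 6.1.3).** A man operated on more than 12 days after the last dose "will be included in the final analysis; however, an additional patient will be accrued as replacement". The reasons given are possible loss of immune infiltration and uniform treatment. The cap is 4. The same section also says that dosed subjects are not replaced for the safety and efficacy endpoints.
- **Lead-in replacements (12.4).** Lead-in men who stop during the DLT period for a reason other than a DLT are replaced for DLT purposes. No cap is stated.
- **Analysis set (12.6.1, repeated in 12.4).** "All patients who receive a dose of ibrutinib will be analyzed for safety and efficacy".
- **UCSF men (12.9).** Data from the 3 men treated at UCSF on the 2-week schedule are shared "under a Data Use Agreement and analyzed under the auspices of this study".
- **Reporting (12.6.2.2).** The responder proportion is given with a 95% confidence interval.

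**The concern.** A fixed responder count has a known error rate only at a known n. Here the late man and his replacement both enter the analysis, so each late operation adds one man to the denominator and one more chance of a responder. The cutoff does not move with n. The same observed count of 4 would then be weaker evidence in a set of 28 than in a set of 24, yet the plan attaches one alpha and one power to both.

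At stake is whether a result of exactly 4 responders can be called positive at the stated level, and whether the trial has the power it claims. The choice of denominator should also not be left open until the tissue results are known.

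**Working it through.** **Inputs.** Null rate 0.05, alternative 0.20, cutoff r = 4, n = 24, one-sided exact binomial, stated alpha 0.044 and power 0.818 (all 12.3). Late-RP cap 4 (12.4). UCSF men 3 (1.4, 3.2, 12.9).

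**Formula.** Alpha = P(X ≥ r | n, 0.05) and power = P(X ≥ r | n, 0.20), with X binomial. For r = 4, each is 1 − [P(0) + P(1) + P(2) + P(3)].

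**Step 1: the plan's own figure at n = 24.**
- Null: 1 − (0.2920 + 0.3688 + 0.2232 + 0.0862) = 0.0298.
- Alternative: 1 − (0.0047 + 0.0283 + 0.0815 + 0.1493) ≈ 0.736.

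The stated 0.044 and 0.818 are not reproduced. Other cutoffs at n = 24 do not help: r = 3 gives 0.116 and 0.886, and r = 5 gives 0.006 and 0.540.

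**Step 2: where the stated pair does hold.** A search over n from 10 to 59 and cutoffs 1 to 11 finds one match for both figures: n = 27, r = 4.
- Null: 1 − (0.2503 + 0.3558 + 0.2434 + 0.1068) = 0.0437.
- Alternative: 1 − (0.0024 + 0.0163 + 0.0530 + 0.1105) ≈ 0.818.

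**Step 3: range of n from late RP alone.** The minimum is 24 and the maximum is 24 + 4 = 28.

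**Step 4: range if other dosed men are counted.**
- 4 late-RP men plus 1 lead-in man replaced for DLT purposes: 24 + 4 + 1 = 29.
- 4 late-RP men plus the 3 UCSF men: 24 + 4 + 3 = 31.

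Because the lead-in replacement route has no cap, 31 is an example and not a ceiling.

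**Step 5: operating characteristics by n.**

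| n | Alpha, cutoff 4 | Power, cutoff 4 | Alpha, cutoff 5 | Power, cutoff 5 |
|---|---|---|---|---|
| 24 | 0.0298 | 0.736 | 0.0060 | 0.540 |
| 25 | 0.0341 | 0.766 | 0.0072 | 0.579 |
| 26 | 0.0387 | 0.793 | 0.0085 | 0.617 |
| 27 | 0.0437 | 0.818 | 0.0100 | 0.652 |
| 28 | 0.0491 | 0.840 | 0.0117 | 0.685 |
| 29 | 0.0548 | 0.860 | 0.0136 | 0.716 |
| 30 | 0.0608 | 0.877 | 0.0156 | 0.745 |
| 31 | 0.0671 | 0.893 | 0.0179 | 0.771 |

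Within 24 to 28, alpha at cutoff 4 passes the stated 0.044 only at n = 28 and stays below 0.05 throughout. It passes 0.05 from n = 29.

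**The case against.** **Late-RP replacement cannot breach 5%.** A reader might infer that keeping and replacing late men is enough to push the test past 5%. It is not: the cap of 4 stops n at 28, where alpha is 0.049. This objection stands in full. Nor does section 12.3 name 5% as the efficacy level. It states 0.044, and the 0.05 in section 12.5.1 belongs to the toxicity stopping rule. I use 5% below only as an assumed conventional limit.

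**The UCSF men are probably not in the test.** Section 12.3 counts 24 men at the maximum tolerated dose (MTD). Section 3.2 labels the UCSF men a phase I cohort, and they had the 2-week schedule. Section 12.9 says their data are analysed in this study, not that they are pooled into the primary test. This has weight, so n = 31 is a possible reading and not the plan's stated intent. The doubt remains because 12.4 and 12.6.1 take every dosed man into the efficacy analysis without limiting this to the MTD cohort.

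**27 might be 24 + 3.** The match at n = 27 invites the inference that the UCSF men were built into the power calculation. No section says so, and the conclusion does not rely on it.

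**The cutoff need not be fixed.** The named method is an exact test, which can be run at whatever n occurs, and 12.6.2.2 plans only a proportion with an interval. That is fair, but 12.3 still gives a count as the criterion of success and never ties it to n. The interval needs a defined denominator too.

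**Evaluable n could also fall below 24.** Section 3.3.1 does not require sufficient tissue for eligibility. This is true, and it adds to the case for defining the set: at n = 23, cutoff 4 gives alpha 0.026 and power 0.704.

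**Dilution.** A reader might also infer that late men pull the responder rate down. The documents give no response rate for them. If 24 men respond at 20% and 4 late men at anything from 0% to 20%, the expected overall rate lies between 4.8/28 = 17.1% and 20%. Even with late men at 5%, the chance of reaching 4 responders rises from 0.736 with 24 men to 0.765 with 28. Retaining all treated men is a defensible choice, stated twice.

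**Conclusion.** The point holds as a gap in definition with a modest numerical effect. Under the late-RP policy alone, n can be 24 to 28. The single cutoff of 4 then carries alpha from 0.030 to 0.049 and power from 0.736 to 0.840, against a stated 0.044 and 0.818 that fit only n = 27. Alpha exceeds the stated level at n = 28 and exceeds 5% at no n in that range. At the planned n of 24 the test is conservative, and power is about 8 percentage points below the stated figure (0.818 − 0.736 = 0.082).

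Alpha above 5% requires n of 29 or more, reached only if lead-in men replaced for DLT purposes or the UCSF men are counted as well. The documents neither direct this nor clearly rule it out.

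These figures assume the cutoff means 4 or more, rates of exactly 5% and 20%, independent responses with a common rate, and every counted man evaluable.

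**What to change.** 1. Define the primary efficacy set once, in section 12.6.1. Say whether late-RP men, lead-in men replaced for DLT purposes and the 3 UCSF men are in or out, and how men without evaluable paired tissue are handled. Align sections 6.1.3, 12.3, 12.4 and 12.9 with it, and reconcile the late-RP exception with the general rule in 12.4 that dosed men are not replaced.
2. Restate alpha and power for the n of that set. For n = 24 and cutoff 4 these are 0.030 and 0.736.
3. Judge the result by the exact one-sided binomial p-value at the actual n, or tabulate the cutoff by n. To hold 5%, the cutoff is 4 up to n = 28 and 5 for n = 29 to 31. To hold the stated 0.044, cutoff 4 serves only up to n = 27.
4. Report the responder rate among men with RP inside the window as a sensitivity analysis beside the all-treated rate. It need not be made primary.

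The cost is wording, settled before tissue results are seen. At n of 29 or more, holding 5% raises the bar by one responder, and power at n = 31 becomes 0.771. The sponsor would also have to accept 0.736 as the power at n = 24.
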